### **3.4.1.2. STUDY DRUG TREATMENT AND IN-HOSPITAL POST-TREATMENT PERIOD**

During the study drug treatment period, assessments should be performed as detailed in the [Schedule of Assessments](#).

If the Day 1, pre-dose assessments will be performed within 3 hours after the screening assessments have been performed, the assessments already done at screening do not need to be repeated and only the additional assessments to be performed on Day 1, pre-dose will need to be performed.

Subjects will receive once-daily administration of study drug on 3 consecutive days. The first dose of study drug is to be administered as soon as possible and within 3 hours after randomization. For all subjects, the exact date and start and end time (and number of interruptions, if any) of the study drug nebulizations will be collected in the eCRF.

Provided that the clinical response criteria have been met, discharge from the hospital can take place per protocol at the Investigator's discretion from dosing Day 2 onwards after all required assessments of the 5 hours ( $\pm 1$  hour) post-dose time point have been completed. Subjects discharged after the second dose must return to the hospital for the third study drug administration (to be administered  $48 \pm 4$  hours after the first dose by the appropriately trained study personnel), and be monitored for a 2-hour pre- and post-dose period.

Subjects who are still hospitalized during the post-treatment period will be followed up twice daily (in the morning and the evening) until the subject is discharged from hospital.

Hospitalization information will be collected during the study drug treatment period and the in-hospital post-treatment period, including occurrence of ICU transfer, apnea episodes, initiation and type of ventilation and hospital/ICU discharge information. Assessment of Clinical Response will be done with collection of date and time of adequate oral feeding to enable discharge as well as adequate stable oxygen saturation on room air of >92% over a period of at least 4 hours. For subjects in the in-hospital post-treatment period, the nasal swab should be collected only on the day of hospital discharge.

All assessments will be performed as specified in the [Schedule of Assessments](#).

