Subjects are screened as soon as possible after arrival to the hospital/emergency unit and randomized shortly thereafter (within 24 hours after arrival). Study drug administration starts with a maximum time interval of 3 hours following randomization. Subsequent doses of study drug are administered at 24-hour intervals ( $\pm 4$  hours) relative to the first dose. On the first 2 dosing days, inpatient hospital stay is required. Provided that the clinical response criteria have been met, discharge from the hospital can take place per protocol at the Investigator's discretion from dosing Day 2 onwards after all required assessments of the 5 hours ( $\pm 1$  hour) post-dose time point have been completed. Subjects discharged after the second dose must return to the hospital for the third study drug administration (to be administered  $48 \pm 4$  hours after the first dose by the appropriately trained study personnel), and be monitored for a 2-3 hour pre-dose and post-dose period (depending on the used protocol version, please see 19.1 for Time and events under different protocol versions) . Subjects who are not discharged from the hospital after completion or premature discontinuation of study drug enter an in-hospital post-treatment period with assessments in the morning and evening. A Follow-Up (FU) visit is scheduled on Day 14 ( $\pm 2$  days), and an End of Study (EOS) visit on Day 28 ( $\pm 2$  days). A detailed description of the scheduled assessments and their timing can be found in Section 19.1.

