## 7.2 Secondary Efficacy Endpoints Evaluation

### 7.2.1 Key Secondary Endpoint: Global Severity Score (GSS)

- As key secondary endpoint, a formal comparison for change from baseline in GSS (see Section 14.3.2 for computation details) to Day 2, 5 hours post dose will be performed using a contrast analysis on a longitudinal mixed model with random factor subject and fixed effects baseline value, treatment group and timepoint including the treatment-by-timepoint interaction term. All data up to and including Day 3 will be used in the longitudinal mixed model. The Kenward-Roger approximation of degrees of freedom will be used. The model will initially be fitted using an unstructured variance-covariance matrix. In case of non-convergence this may be replaced with a autoregressive variance covariance matrix with heterogeneous variance (ARH) to achieve convergence of the model. The individual pair-wise comparisons will be reported. No formal multiplicity correction will be performed. This comparison will be performed for mITT, RSV infected and PP population.
- For GSS and each of the GSS subitems where GSS is not missing, descriptive statistics will be provided for the actual values and the change from baseline for all planned timepoints. In addition to these planned timepoints, a separate timepoint (Day of hospital discharge) will be created using the last value on the date of discharge from the hospital for GSS summary tables.
- The mean GSS  $\pm$  SE will presented graphically over time (excluding the in-hospital post-treatment assessments), as well as the mean change from baseline  $\pm$  SE. Two bar charts will be provided. One bar chart will present the mean GSS and contributing subitems at all timepoints up to Day 3, 2 hours post dose. The second bar chart will present the mean GSS and contributing subitems over the whole study period (excluding the in-hospital post-treatment timepoints), but will for the first 3 days only include the pre-dose assessments.

Descriptive statistics and figures will be performed on both mITT and RSV infected population

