#### 14.2.2 Global Severity Score (GSS)

GSS will be calculated by summing the scores of 7 individual items (see below). Maximum score is 20 with higher score indicating a more severe disease.

For the computation of the baseline GSS, the baseline value of each individual item is first identified (some may be from Day 1 pre-dose and others from screening). The individual item baseline values are then summed to obtain the baseline GSS.

Apnea, hospital stay, oxygen supplementation, and ventilation will be considered respectively to have occurred at the considered visit and time point if they are reported over a period that covers at least partly the time interval defined for this visit using following definitions for time intervals:

- for baseline : from hospital admission to first study drug administration,
- for post-baseline visits and timepoints during treatment as:
  - starting from the minimum between:
    - the end of the previous interval,
    - the earliest date and time a GSS component was assessed at the considered visit and timepoint, and
    - 1 minute before the latest date and time a GSS component was assessed at the considered visit and timepoint

- - ending at the latest date and time a GSS component was assessed at the considered visit and timepoint.
- for all ‘Post-Treatment Day n’ visits:
  - the “MORNING” timepoint will be assigned to time interval 00:00 – 11:59 of the date of the considered visit and timepoint
  - the “EVENING” timepoint will be assigned to time interval 12:00 – 23:59 of the date of the considered visit and t timepoint
- The “Follow-UP” visit and unscheduled post-treatment visits will be assigned to time interval 00:00 – 23:59 of the date of the considered visit and timepoint. This implies that there will be a gap between the follow-Up visit and the previous timepoint, and that every hospitalization / apnea / ventilation / oxygen supplementation recorded that would be entirely within that gap will not be taken into account into GSS score computed at any timepoint.

This implies that a recorded item (hospitalization / apnea / ventilation / oxygen supplementation) may contribute to more than one time interval for the GSS calculation.

Item	Number of Points	Description
Feeding	0	Adequate oral feeding
	1	No adequate oral feeding, occasional breaks during feeding
	2	No adequate oral feeding, frequent breaks during feeding
	3	No adequate oral feeding, unable to feed, or on feeding support

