Medical interventions	0	Not hospitalized
	1	Hospitalization without O 2 supplementation
	2	Conventional oxygen supplementation
	3	Non-invasive respiratory support or invasive ventilation
Respiratory distress	0	RDAI = 0
	1	RDAI ≥ 1 to < 6
	2	RDAI ≥ 6 to ≤ 11
	3	RDAI > 11
Respiratory rate	0	<2 months: ≤50 bpm; 2-<6 months: ≤45 bpm; 6-<12 months: ≤40 bpm; 12-24 months: ≤35 bpm
	1	<2 months: >50 to ≤60 bpm; 2-<6 months: >45 to ≤55 bpm; 6-<12 months: >40 to ≤50 bpm; 12-24 months: >35 to ≤45 bpm
	2	<2 months: >60 to ≤70 bpm; 2-<6 months: >55 ≤ 60; 6-<12 months: >50 to ≤55 bpm; 12-24 months: >45 to ≤50 bpm
	3	<2 months: >70 bpm; 2-<6 months: >60 bpm; 6-<12 months: >55 bpm; 12-24 months: >50 bpm
Apnea	0	No apnea episode
	3	Apnea episode
General appearance a	0	Active, playing/ content/ interactive and happy
	1	Less active/ mildly irritable/ less interactive or responsive
	2	Less active/ moderately irritable/ less interactive or responsive
	3	Not active/ Severely irritable/ Not interactive or not responsive

Note: In case worst item is less active and/or less interactive: if both are present: 2 points; if only one of both is present and the highest: 1 point

Body Temperature	0	<37,0°C: (measured axillary); <37,5°C (measured by other method)
	1	≥37,0°C but <38°C (measured axillary); ≥37,5°C but <38,5°C (measured by other method)
	2	≥38°C (measured axillary); ≥38,5°C (measured by other method)

a Assessed through activity, irritation and interest in environment (worst of the three items will be used for attributing the points)

Following imputation will be done for missing data :

- For General appearance, scoring will be done only on completed items and only the worst item is used for scoring.
- If more than two individual items (i.e., feeding, medical intervention, RDAI, respiratory rate, general appearance and body temperature) are missing at a given timepoint GSS will be set to missing for this timepoint
- If maximum 2 individual items are missing at a timepoint, missing items will be imputed using LOCF approach and the GSS will be calculated after imputation of the individual item(s).
- 

Imputed items will be flagged in the listings.

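### The GSS interval rule scores infants discharged on Day 2 as still hospitalised at Day 3 pre-dose, which creates an artificial fall across the third inhalation

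*SAP*

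**What the plan says.** SAP 14.2.2 builds the GSS from seven items. Four inputs are recorded as periods or episodes: hospital stay, oxygen supplementation, ventilation and apnea. They count at a visit and timepoint "if they are reported over a period that covers at least partly the time interval defined for this visit".

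For post-baseline timepoints during treatment, the interval starts at the minimum of three times. The first is "the end of the previous interval"; the other two are assessment times at the timepoint itself. The interval closes as follows: "ending at the latest date and time a GSS component was assessed at the considered visit and timepoint". The SAP adds that one record may count in more than one interval.

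The Medical interventions item gives 0 for "Not hospitalized", 1 for hospitalisation without oxygen, 2 for conventional oxygen and 3 for ventilatory support.

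On discharge, Protocol 3.4.1.2 says "discharge from the hospital can take place per protocol at the Investigator's discretion from dosing Day 2 onwards after all required assessments" of the 5 h post-dose timepoint are complete, provided the clinical response criteria are met. SAP 4.1 repeats this. An infant discharged after the second dose returns for the third, and the Protocol's dosing rationale (3.1.2) calls that return an ambulatory visit.

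SAP 7.2.1 puts all data through Day 3 into the GSS mixed model and tests the change to Day 2, 5 h. It also plans descriptive tables, mean plots and two bar charts. The second bar chart "will for the first 3 days only include the pre-dose assessments".

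**The concern.** Looking back over the interval is sensible for an episodic event such as apnea, which a spot assessment would miss. Hospital stay is different: it is a state with a recorded end. Under the overlap rule, the last hours of a stay on Day 2 set the score for an assessment made the next day, when the infant is living at home. The lowest level of the item is then out of reach at Day 3 pre-dose for an infant discharged per protocol on Day 2. That infant gets the same hospitalisation score as one who never left.

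Two things are at stake. Day 3 pre-dose values are too high in every arm, and more so in an arm with more early discharge. The correction then appears at the next timepoint, just after the third inhalation, where a reader could take a scoring artefact for an acute response to the dose.

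The affected outputs include topline items: Table 14.2.1.7, the change-from-baseline plots (Figures 14.2.1.11 and 14.2.1.13) and the bar charts (Figures 14.2.1.14 and 14.2.1.15). Subgroup Table 14.2.8.2 is affected as well. The second bar chart shows only pre-dose values on Days 1-3 and omits the in-hospital post-treatment timepoints, so a Day 2 discharge cannot appear there as 0 before the Follow-up visit.

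**Working it through.** The plan states no figure to reproduce here; the check applies the scoring rule itself.

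**Rule (SAP 14.2.2).** For an on-treatment timepoint k:
- start(k) = min{end(k-1), earliest component time at k, latest component time at k minus 1 minute}
- end(k) = latest component time at k
- hospital stay counts if any part of it lies between start(k) and end(k)

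**General argument**
1. Day 3 pre-dose: start ≤ end of the Day 2, 5 h interval, which is the last Day 2, 5 h component.
2. Per-protocol discharge is later than that component.
3. The stay therefore runs into the Day 3 pre-dose interval, and the item is at least 1.
4. Day 3, 2 h: the interval opens at the last Day 3 pre-dose component, after discharge. With no new stay recorded, the item is 0. Feeding, general appearance and temperature are all scheduled at this timepoint, so a GSS is available.

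**Illustrative timeline (hours from first dose; times assumed within the protocol windows)**
- Components assessed: Day 2, 5 h at 29.4-29.8; Day 3 pre-dose at 46.5-47.8; Day 3, 2 h at 50.4-50.8.
- Day 3 pre-dose interval: start = min(29.8, 46.5, 47.78) = 29.8; end = 47.8.
- Day 3, 2 h interval: start = min(47.8, 50.4, 50.78) = 47.8; end = 50.8.

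| Case | Day 3 pre-dose | Day 3, 2 h |
|---|---|---|
| Discharged 10 min after the last Day 2, 5 h component, no oxygen | 1 | 0 |
| Oxygen off at 29.0, discharged at 35 | 1 | 0 |
| Oxygen off at 30.5, discharged at 35 | 2 | 0 |
| In hospital throughout, no oxygen | 1 | 1 |

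Scored by status at assessment, the first three rows would be 0 and 0.

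**Sweep.** In 200,000 random timelines (doses at 24±4 h and 48±4 h, assessments at 5±1 h and 2±0.5 h, no oxygen, discharge placed between the two assessments), the item was 1 at Day 3 pre-dose and 0 at Day 3, 2 h in all 200,000.

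**Size.** Let p be the share of an arm discharged on Day 2 and q the share discharged on Day 2 whose oxygen ran past the last Day 2, 5 h component. Then:
- overstatement of the arm mean at Day 3 pre-dose = p × 1 + q × 1 ≥ p
- p = 5%: at least 0.05 points; p = 25%: at least 0.25 points (p is assumed; the documents do not give it)
- distortion of the arm difference, with q equal in the two arms = p(active) - p(placebo). For an assumed 25% v 10%, 0.25 - 0.10 = 0.15 points against the active arm; for equal shares, 0.

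For scale, the GSS maximum is 20 and the planning SD is 3.2, so 0.25 points is 0.25/3.2 = 0.08 SD.

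**The case against.** The best defence is that this is a disclosed convention. One rule covers all four inputs so that events between assessments are not lost, the infant really was in hospital for part of the interval, and the SAP says a record may count more than once. That shows the carry-over was foreseen in general. It does not address the specific result that the lowest level of the item cannot be reached at Day 3 pre-dose after a per-protocol Day 2 discharge.

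Other parts of the defence stand, and they rule out stronger readings that a reader might infer:

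- **That the key secondary test is biased.** The only GSS test is at Day 2, 5 h, before any per-protocol Day 2 discharge. Day 3 rows reach it only through the shared model. In a two-arm simulation (unstructured covariance, 45 per arm, 25% v 10% discharged, 0-15% missing, other inputs assumed, 150 runs per setting), the contrast moved by at most 0.002 points on average and by less than 0.08 in any run.
- **That the distortion is a given fraction of the planned 2-point effect.** That target is defined for Day 2 post-dose. No target exists for Day 3.
- **That the benefit of early discharge is lost.** Credit is delayed to Day 3, 2 h, which is in the model, the table, the mean plots and the first bar chart. Length of stay, time from first dose to discharge and time to clinical response are analysed separately.
- **That the drop is always exactly 1 point.** One point is a minimum, and the fall to 0 requires that the ambulatory return is not entered as a hospital stay, which the SAP does not state.

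**Conclusion.** The point holds for the Day 3 pre-dose GSS and outputs built on it. An infant discharged per protocol on Day 2 and assessed at Day 3 pre-dose scores at least 1 on Medical interventions, and 2 if conventional oxygen was still running after the last Day 2, 5 h assessment. If the ambulatory return is not recorded as a hospital stay, the item is 0 at Day 3, 2 h, giving an artificial drop across the third dose. Exceptions are marginal, such as a discharge time equal to the last Day 2, 5 h assessment, or a missing discharge time imputed to before it.

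The overstatement of each arm's Day 3 pre-dose mean is at least the share discharged on Day 2: 0.05-0.25 points under the assumed 5-25%. It occurs in all arms and biases the comparison at that timepoint only if early discharge differs by arm. The descriptives, mean plots, bar charts and Day 3 rows of the mixed model are affected. The documents do not support carrying this over to the Day 2, 5 h contrast, which is not materially changed. This is a minor point that is worth correcting because the correction is cheap.

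**What to change.** In SAP 14.2.2, for on-treatment timepoints:

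1. Score the whole Medical interventions item 0 when the discharge date and time precede the first GSS component assessed at that timepoint and the infant has not been readmitted, regardless of hospital stay or oxygen earlier in the interval. Changing the hospitalisation level alone is not enough: oxygen left on the overlap rule would still give some discharged infants a 2.
2. If the discharge time is missing, impute it as in SAP 14.2.9 (18:00).
3. State that an ambulatory Day 3 dosing visit is not a hospital stay.
4. Keep the overlap rule for apnea and for infants still in hospital.

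The cost is a short paragraph in the SAP and one derivation step. Hospital discharge information is already collected, so no new data are needed. The change applies identically to all arms and should be made before unblinding.

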### 14.2.3 Respiratory Distress Assessment Instrument (RDAI)

RDAI is a 17-point score based on wheezing and retraction (see below).

Variable	Number of Points					Maximum Points
	0	1	2	3	4	
Wheezing						
Expiration	None	End	1/2 period	3/4 period	All	4
Inspiration	None	Part	All	NA	NA	2
Location	None	Segmental ≤ 2 of 4 lung fields	Diffuse ≥ 3 of 4 lung fields	NA	NA	2
Retractions						
Supraclavicular	None	Mild	Moderate	Marked	NA	3
Intercostal	None	Mild	Moderate	Marked	NA	3
Subcostal	None	Mild	Moderate	Marked	NA	3

NA = not applicable

The RDAI score is the sum of the row scores, with total range 0 to 17; higher scores indicate more severe disease.

No imputation of missing data will be performed

#### 14.2.4 Respiratory Assessment Change Score (RACS)

The RACS score is the sum of the change from baseline in the RDAI score and a standardised score for the change from baseline in respiratory rate. The change in respiratory rate is assigned 1 point per each 10% change in the respiratory rate.

A decrease in the sum of the RDAI and the respiratory rate during the study period is recorded as a negative RACS, meaning an improvement.

If change in respiratory rate is missing, missing value will be imputed using an LOCF imputation. Imputed values will be flagged in the listings.

#### 14.2.5 Respiratory symptoms score

Based on the information collected in the diary (regarding cough, trouble breathing and wheezing), a respiratory symptoms score will be calculated. The score will range from 0 to 5. A subitem score for each of the respiratory symptoms (cough, trouble breathing and wheezing) will be calculated using the following scoring:

Severity	Score
No	0
Very mild	1
Mild	2
Moderate	3
Severe	4
Very severe	5

The respiratory symptoms score will be calculated by taking the sum over all non-missing subitems and dividing by the number of non-missing items. In case more than 1 subitem is missing the total score will also be set to missing.

#### 14.2.6 Duration of supplemental oxygen therapy

This is based on concomitant medication records.

For Baseline assessment a subject is considered being on oxygen supplementation at baseline if oxygen was received between hospital admission and the first dose of study medication. For this derivation, both prior and concomitant medications are considered

Total duration will be calculated as the total number of hours (taking into account the sum of the actual time windows the concomitant medication was received) using concomitant treatment coded as "Oxygen" from admission until trial termination and from first dose until trial termination. Missing information on concomitant medication records will be imputed in the following way

- If start time is missing: impute with 0:00 .

- If end time is missing: impute with 23:59.
- If start day/month is missing: impute with first day (01) / month (Jan) if this falls within trial window, otherwise impute with day/month of first contact in the trial.
- If end day/month is missing: impute with last day (31) / month (Dec) if this falls within trial window, otherwise impute with day/month of trial termination.

In case of overlapping records, the duration will be calculated only once for the overlapping part of the records.

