## 7.3 Other Efficacy Analyses

- Evolution over time in clinical symptoms will be evaluated. The body temperature and respiratory rate (actual values, change from baseline and percent change from baseline) will be summarized descriptively over time. Frequency tabulations will be provided to summarize the feeding, respiratory distress parameters (Wheezing (during inspiration/expiration), lung fields affected, crackles/crepitations, respiratory muscle retractorations (supravascular, intercostal and subcostal) , cough and general appearance of the subject over time. Respiratory rate and body temperature will also be presented graphically in mean  $\pm$  SE plots (excluding the in-hospital post-treatment timepoints).
- Respiratory Distress Assessment Instrument (RDAI) and Respiratory Change Score (RACS) will be calculated (see Section 14.2.3 and 14.2.4 for calculation method, respectively) . Actual values (RDAI, RACS) and changes from baseline (RDAI) will be summarized over time using descriptive statistics (both subitem and totals). RDAI, change from baseline in RDAI and RACS will also be presented graphically in mean  $\pm$  SE plots (excluding the in-hospital post-treatment timepoints). Similar to GSS, bar charts will be generated for RDAI to visualize contributing subitems.
- Length of hospital stay (in days – see section 14.2.9 for calculation method) defined as time between admission and discharge for the initial hospitalization will be summarized as descriptive statistics and using KM estimates. In case of missing discharge information the subject will be censored on date(time) of trial termination.
- The time between first study drug administration and discharge (in days) for the initial hospitalization will be summarized as descriptive statistics and using KM estimates. In case of missing discharge information the subject will be censored on date(time) of trial termination.

- Length of hospital stay for RSV: The time between hospital admission and discharge (in days) excluding prolongation due to SAE other than RSV worsening. Time will be summarized as descriptive statistics and using KM estimates. In case of missing discharge information the subject will be censored on date(time) of trial termination. If needed time will be imputed with 18u00 (see section 14.2.10 for calculation details).

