- Duration of severe disease (in hours) defined as the time between hospital admission and achieving clinical response will be summarized using KM estimates. The time to event for subjects with missing data and/or who did not reach the clinical response during the trial will be censored at the last nonmissing assessment of blood oxygen level in the vital signs domain (VSTESTCD=OXYSAT) or assessment of adequate oral feeding (DCTESTCD=FEDADQ).
- A cross-tabulation will present the proportion of subjects on oxygen supplementation at baseline versus post-baseline (i.e., any time between first dose date/time and end of study) per treatment group. Additionally, duration of supplemental oxygen therapy (in hours) defined as total time of reported oxygen supply will be calculated based on concomitant medication (CM) records with coded term 'Oxygen' and summarized descriptively. In case of missing CM information a worst case imputation will be applied (see section 14.2.6 for calculation and imputation rules).
- A cross-tabulation will present the proportion of subjects on feeding support at baseline versus post-baseline (i.e., any time between first dose date/time and end of study) per treatment group. Additionally, duration of feeding support (in hours) defined as total time of reported feeding support will be calculated based on concomitant medication records. In case of missing CM information a worst case imputation will be applied (see section 14.2.7 for calculation and imputation rules).
- Incidence of initiation of invasive and non-invasive ventilation (continuous positive airway pressure, bilevel positive airway pressure and high flow ventilation) as well as incidence of apnea will be tabulated. Additionally, duration of invasive and non-invasive ventilation will be summarized descriptively (in hours - see Section 14.2.8 for calculation method).
- The number and percentage of subjects transferred to ICU and duration of ICU stay (in days – see section 14.2.9 for calculation method) will be summarized using descriptive statistics
- Parent(s)/Caregiver(s) diary assessment will be reported as
  - Frequency tabulation over time (condition as before RSV, severity of cough, severity trouble breathing and severity wheezing).

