#### 14.2.7 Duration of feeding support

This is based on concomitant medication records.

For Baseline assessment a subject is considered being on feeding support at baseline if support was received between hospital admission and the first dose of study medication. For this derivation, both prior and concomitant medications are considered

Following coded terms will be considered for feeding support provided the route of administration is intravenous or nasogastric.

AMINO ACIDS NOS  
AMINOVEN  
CALCIUM GLUCONATE  
DEXTROSE AND SODIUM CHLORIDE INJECTION  
DEXTROSE IN LACTATED RINGER'S  
ELECTROLYTES NOS  
ELECTROLYTES NOS W/GLUCOSE  
GLUC5% W/RINGER BAXTER  
GLUCOSE  
GLUKOSALINA /06282701/  
INFANT FORMULAS  
ISOLYTE /06504901/  
ISOLYTE P DEXTROSA  
JONOSTERIL /01263001/  
MAGNESIUM SULFATE  
MATERNA /02266601/  
OSMOTAN  
POTASSIUM CHLORIDE  
PROTEIN HYDROLYSATE  
RICE /08368701/  
RINDEX /07339201/  
RINGER-LACTATE

SODIUM CHLORIDE  
SODIUM GLYCEROPHOSPHATE

Total duration will be calculated as the total number of hours (taking into account the sum of the actual time windows the concomitant medication was received) using concomitant treatment from the above list from admission until trial termination and from first dose until trial termination. Missing information on concomitant medication records will be imputed in the following way

- If start time is missing: impute with 0:00 .
- If end time is missing: impute with 23:59.
- If start day/month is missing: impute with first day (01) / month (Jan) if this falls within trial window, otherwise impute with day/month of first contact in the trial.
- If end day/month is missing: impute with last day (31) / month (Dec) if this falls within trial window, otherwise impute with day/month of trial termination.

In case of overlapping records, the duration will be calculated only once for the overlapping part of the records.

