**14.2.8 Duration and type of ventilation**

This is based on CRF procedure information (PR domain). Total duration of invasive and non-invasive ventilation (in hours) will be calculated as the sum of all durations from first dose until trial termination per category and subject. Missing information on individual records will be imputed in the following way

- If start time is missing: impute with 0:00 .
- If end time is missing: impute with 23:59.
- If start day/month is missing: impute with first day (01) / month (Jan) if this falls within trial window, otherwise impute with day/month of first contact in the trial.
- If end day/month is missing: impute with last day (31) / month (Dec) if this falls within trial window, otherwise impute with day/month of trial termination.

In case of overlapping records, the duration will be calculated only once for the overlapping part of the records. .

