**14.2.9 Duration of hospital/ICU stay:**

Defined as the time between hospital admission and discharge (in days)

- If start time is missing: impute with 0:00.
- In case end time is missing: impute with 18:00 .
- If start day/month is missing: impute with first day (01) / month (Jan) if this falls within trial window, otherwise impute with day/month of first contact in the trial.
- If end day/month is missing: impute with last day (31) / month (Dec) if this falls within trial window, otherwise impute with day/month of trial termination.

In case the subject is still hospitalized at the end of the trial, the trial termination date will be used.

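### Oxygen and feeding-support hours are cut at trial termination and averaged as finished episodes, so an infant who leaves the study early on support counts with the shortest possible duration

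*SAP*

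**What the plan says.** For oxygen, SAP 14.2.6 adds up the recorded time windows "from admission until trial termination and from first dose until trial termination". For feeding support, 14.2.7 does so "using concomitant treatment from the above list from admission until trial termination and from first dose until trial termination". For ventilation, 14.2.8 says the total "will be calculated as the sum of all durations from first dose until trial termination per category and subject". In all three, a missing end day or month becomes the last day or month if that lies inside the trial window; "otherwise impute with day/month of trial termination".

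SAP 7.3 summarises oxygen and ventilation time descriptively. Table 14.2.6.4 (oxygen) and Table 14.2.6.5 (feeding support) list descriptive statistics only, and Table 14.2.6.8 (ventilation) has frequencies and descriptive statistics. None has a censored count. For oxygen and feeding support, 7.3 adds: "In case of missing CM information a worst case imputation will be applied". It says nothing of the kind for ventilation.

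Hospital stay and time from first dose to discharge get Kaplan-Meier estimates beside descriptive statistics: "In case of missing discharge information the subject will be censored on date(time) of trial termination". For the duration itself, 14.2.9 says: "In case the subject is still hospitalized at the end of the trial, the trial termination date will be used".

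**The concern.** For an infant withdrawn from the study, trial termination is read here as the withdrawal date, which can fall in the first days. Protocol 3.2.3 requires withdrawal when the investigator judges it best for safety, or when consent is withdrawn. After consent is withdrawn no further assessments are made (Protocol 3.4.1.3). Hours on support after that point are unseen, yet the hours before it are averaged as if the episode had ended.

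If infants who leave on support are sicker than the rest, the arm that loses more of them would appear to need less support. Protocol 3.1.2 names the need for medical interventions among the measures of clinical impact, so the direction of the error matters even without a test.

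**Working it through.** The plan states no figure on this point, so there is none to reproduce. The check compares the rules and then illustrates size on assumed values.

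**1. Treatment of an episode still open at termination**

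| Measure | Summary | Open episode |
|---|---|---|
| Oxygen (14.2.6, Table 14.2.6.4) | descriptive | counted as complete |
| Feeding support (14.2.7, Table 14.2.6.5) | descriptive | counted as complete |
| Ventilation (14.2.8, Table 14.2.6.8) | descriptive | counted as complete |
| Hospital stay, first dose to discharge (7.3, 14.2.9, 14.2.11) | descriptive and Kaplan-Meier | censored in Kaplan-Meier; termination date used in the descriptives |
| ICU stay (7.3, 14.2.9, Table 14.2.6.10) | descriptive in 7.3; Kaplan-Meier added in the table index | as for hospital stay |

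**2. What the fallback date does.** Let support start at s and trial termination be w. The imputed duration is w − s.
- Support ended in the window at an unknown time: the true end is at or before w, so w − s is the longest possible value. Worst case is a fair name.
- Support ongoing at w: the true end is at or after w, so w − s is the shortest possible value.

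The rule returns the same number in both situations and the tables do not separate them.

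**3. One arm of 45.** Assume k infants leave at 24 h on oxygen with true duration D, and the others average 72 h.
- Mean as planned = [(45 − k) × 72 + k × 24]/45. For k = 3: (3024 + 72)/45 = 68.8 h.
- True mean = [(45 − k) × 72 + k × D]/45. For k = 3 and D = 120 h: (3024 + 360)/45 = 75.2 h. For D = 240 h: (3024 + 720)/45 = 83.2 h.
- For k = 1 and D = 120 h: 3192/45 = 70.9 h against 3288/45 = 73.1 h.

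**4. Relative loss in the mean.** Assume exponential support times with mean M and a share d of infants withdrawn uniformly over 0–72 h. A withdrawn infant is still on support with probability p = (M/72)(1 − e^(−72/M)) and then loses M hours on average, so the relative loss is d × p.

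| M (h) | p | d = 2% | d = 5% | d = 15% |
|---|---|---|---|---|
| 48 | 0.518 | 1.0% | 2.6% | 7.8% |
| 72 | 0.632 | 1.3% | 3.2% | 9.5% |
| 120 | 0.752 | 1.5% | 3.8% | 11.3% |

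A simulation with durations capped at 27 days agrees (11.2% in the last cell).

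**5. Median.** In that simulation, at M = 72 h and d = 15%, the median is 49.9 h uncut, 43.1 h cut, and 49.9 h by Kaplan-Meier with censoring at withdrawal. Kaplan-Meier recovers the uncut value because withdrawal was simulated as unrelated to support time.

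**The case against.** The other side has several good points.

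- **Worst-case wording.** A reader might infer that the SAP's imputation is the reverse of worst case. The documents do not support that. The phrase covers only missing medication records for oxygen and feeding support, and for support that ended in the window the rule gives the longest value. It is never applied to ventilation.
- **Ventilated infants.** Under Protocol 3.3.8, infants who start ventilation stop study drug but should stay in the study through the follow-up and end-of-study visits. Ventilation is therefore the least exposed of the three.
- **Who is affected.** Infants withdrawn because dosing could not start on Day 1 are outside the mITT population used for these tables. An infant still on support near Day 28 gets a long value. Only early withdrawal on support matters.
- **Other analyses.** SAP 7.2.2.1 already gives censored Kaplan-Meier times to adequate saturation and to adequate feeding, at secondary level. SAP 7.3 does so for duration of severe disease. Listings of termination, oxygen and feeding support would let a reader find the open episodes.
- **Size.** The 15% drop-out in the sample size also covers false-positive RSV tests (Protocol 3.1.2), so it is an upper illustration. The figures above are shifts within one arm. A reader might infer a bias towards a particular arm, but that needs unequal withdrawal, which the documents do not show.

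All of this narrows the point. It does not change what the support-duration tables do: they mix finished and unfinished episodes without saying so.

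**Conclusion.** The point holds in limited form. Oxygen and feeding-support hours, and with less exposure ventilation hours, are truncated at trial termination and summarised as complete, although the SAP censors comparable durations elsewhere. The error is confined to infants who leave the study early while on support, and for them the recorded value is a lower bound.

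The size is unknown. The range of about 1–1.5% of the mean at 2% withdrawn to 8–11% at 15% rests on assumed exponential durations with means of 48–120 h and withdrawal within 72 h. These are descriptive 'other' endpoints with no planned test, and neither the primary nor the key secondary analysis is affected. The change is worth making because it is cheap and follows the SAP's own method.

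**What to change.** Amend the SAP as follows.

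1. Flag support ongoing at trial termination. Report the number of such infants per arm beside the summed-hours descriptives for oxygen, feeding support and ventilation. Report likewise those still in hospital or ICU beside the stay descriptives.
2. For oxygen and feeding support, add Kaplan-Meier time from first dose to final cessation among infants on support at baseline, censored at termination when ongoing. Require a record open at first dose, because the SAP's baseline definition also counts support that stopped before dosing. State a rule for death, and note that censoring may be informative if sicker infants withdraw; SAP 7.1 already names the corresponding assumption for the log-rank test.
3. Limit the worst-case wording to partial dates within the trial window.

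Two tempting alternatives should be avoided. Restricting means to infants with an observed end drops the longest episodes: with 44 infants averaging 72 h and one on oxygen for 672 h (assumed), the mean is (3168 + 672)/45 = 85.3 h under the SAP but 72.0 h after restriction. Time from first dose to cessation does not suit ventilation, because infants already ventilated are excluded at entry.

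The cost is SAP wording and a few table rows from dates already collected, with no protocol change. One limit remains: time to final cessation differs from total hours when support is intermittent, so the two should be shown side by side.
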